APPENDIX B: DEFINITIONS43

APPENDIX C: REFERENCES.....50

LIST OF TABLES AND FIGURES

Table 1: Alterra Device Sizing 13

Table 2: Recommended Concomitant Medical Therapy19

Table 3: Schedule of Events23

Figure 1: Edwards Alterra Adaptive PreStent.....12

Figure 2: Edwards Alterra Delivery System 13

PROTOCOL SYNOPSIS

| | |
|----------------------------|--|
| Title | ALTERRA Multicenter Study of Congenital Pulmonic Valve Dysfunction Studying the SAPIEN 3 Transcatheter Heart Valve with the Alterra Adaptive Presept |
| Purpose | To demonstrate the safety and effectiveness of the Edwards Alterra Adaptive Presept in conjunction with the Edwards SAPIEN 3 Transcatheter Heart Valve (THV) System in subjects with a dysfunctional right ventricular outflow tract/pulmonary valve (RVOT/PV) who are indicated for treatment of pulmonary regurgitation (PR) |
| Study Devices | 
• Edwards Alterra Adaptive Presept and delivery system• Edwards SAPIEN 3 THV with the associated delivery systems |
| Study Design | Single arm, prospective, multicenter study. A separate registry will be conducted to evaluate the Pulmonic Delivery System (PDS) for delivery of the SAPIEN 3 THV. |
| Study Population | The study population will be comprised of subjects with a dysfunctional RVOT/PV, who are indicated for treatment of moderate to severe PR. |
| Sample Size | Up to 60 subjects will be enrolled in the main cohort. Subjects enrolled under earlier versions of the protocol (Early Feasibility Study versions 1.0 and 2.0) will count towards enrollment. Twenty-five additional subjects will be enrolled in the PDS Registry. |
| Study Sites | Up to 25 participating sites in the US and Canada |
| Assessment Schedule | Screening/baseline, discharge, 30 days, 6 months, 12 months and annually thereafter through 10 years |
| Primary Endpoint | Main Cohort: THV dysfunction at 6 months. THV dysfunction is defined as a non-hierarchical composite of: 
• RVOT/PV reintervention• Moderate or greater total PR via Transthoracic Echocardiography (TTE)• Mean RVOT/PV gradient \geq 35 mmHg via TTE PDS Registry: Acute PDS Success, defined as a non-hierarchical composite of: 
• Single THV implanted in the desired location• Right ventricle to pulmonary artery (RV-PA) peak-to-peak gradient < 35 mmHg post-THV implantation• Less than moderate total PR by discharge TTE (or earliest evaluable TTE) |

Secondary Endpoints

- Free of SAPIEN 3 / Alterra explant at 24 hours post-implantation

Main Cohort:

The following secondary endpoint will be evaluated for labeling purposes:

- Improvement in total PR from baseline to 30 days

Additional Safety and Effectiveness Outcomes

The following additional outcomes will be evaluated:

Main Cohort:

- Improvement in tricuspid regurgitation (TR) from baseline to 30 days and 6 months by TTE for subjects with TR of mild or greater at baseline
- Major vascular complications at 30 days and 6 months
- Life-threatening or disabling bleeding at 30 days and 6 months
- Alterra embolization at 30 days and 6 months
- THV embolization at 30 days and 6 months
- Alterra fracture that led to reintervention at 30 days and 6 months
- THV frame fracture that led to reintervention at 30 days and 6 months
- All-cause mortality at 30 days and 6 months
- Acute Device Success, defined as a non-hierarchical composite of:
 - Single Alterra deployed in the desired location
 - Single THV implanted in the desired location within Alterra (staged procedures allowed)
 - RV-PA peak-to-peak gradient < 35 mmHg post-THV implantation
 - Less than moderate total PR by discharge TTE (or earliest evaluable TTE)
 - Free of Alterra explant at 24 hours post-implantation

PDS Registry:

- Improvement in tricuspid regurgitation (TR) from baseline to 30 days by TTE for subjects with TR of mild or greater at baseline
- Major vascular complications at 30 days
- Life-threatening or disabling bleeding at 30 days
- Alterra embolization at 30 days
- THV embolization at 30 days

Inclusion Criteria

1. The candidate/candidate's legal guardian has been informed of the nature of the study, agrees to its provisions and has provided written informed consent
2. Weight is ≥ 20 kg (≥ 44 lbs)

| | |
|----------------------------|---|
| | 
3. RVOT/PV with moderate or greater PR by TTE4. RVOT/PV proximal and distal landing zone diameter ≥ 27 mm and ≤ 38 mm, and minimum of 35 mm from contractile tissue to lowest pulmonary artery takeoff |
| Exclusion Criteria | 
1. Active infection requiring current antibiotic therapy (if temporary illness, patient may be a candidate 2 weeks after discontinuation of antibiotics)2. History of or active endocarditis (active treatment with antibiotics) within the past 180 days3. Leukopenia (WBC < 2000 cells/μL), anemia (Hgb < 7 g/dL), thrombocytopenia (platelets $< 50,000$ cells/μL) or any known blood clotting disorder4. Inappropriate anatomy for introduction and delivery of Alterra or the SAPIEN 3 THV5. Need for concomitant atrial septal defect or ventricular septal defect closure or other concomitant interventional procedures other than pulmonary artery or branch pulmonary artery stenting or angioplasty6. Interventional/surgical procedures within 30 days prior to the Alterra or valve implant procedure7. Any planned surgical, percutaneous coronary or peripheral procedure to be performed within the 30-day follow-up from the Alterra or valve implant procedure8. History of or current intravenous drug use9. Major or progressive non-cardiac disease resulting in a life expectancy of less than one year10. Known hypersensitivity to aspirin or heparin and cannot be treated with other antiplatelet and/or antithrombotic medications11. Known hypersensitivity to nitinol, cobalt-chromium, nickel or contrast media that cannot be adequately pre-medicated12. Currently participating in an investigational drug or another device study [Note: Trials requiring extended follow up for products that were investigational, but have since become commercially available, are not considered investigational devices.]13. Positive urine or serum pregnancy test in female patients of child-bearing potential14. Renal insufficiency (creatinine > 3.0 mg/dL) and/or renal replacement therapy |
| Statistical Methods | 
Main Cohort:
 
For the primary endpoint of THV dysfunction at 6 months, an exact binomial 95% confidence interval (CI) for the percent of subjects with THV dysfunction will be calculated and compared to the performance goal of 25%. If the
 |

upper bound of the CI is below 25% then the performance goal will be considered to be met.

PDS Registry:

Descriptive statistics will be provided; no formal hypothesis testing will be conducted.

Study Principal Investigator [name], FACC, FSCAI
Cedars-Sinai Heart Institute

Sponsor Edwards Lifesciences
[name]
[name]

INVESTIGATOR SIGNATURE PAGE

1 INTRODUCTION

1.1 Background

Congenital heart defects (CHD) can be complex, involving structures of either the right and/or left heart and are reported in approximately eight of every 1000 newborns. Right ventricular outflow tract (RVOT) defects such as pulmonary valve stenosis, Tetralogy of Fallot, and double outlet right ventricle are common in this population and may represent as many as 20% of those with CHD. Initial surgical correction of these lesions often involves relief of RVOT obstruction often using a combination of muscular resection, pulmonary valvotomy/valvectomy and a transannular patch. While surgical correction of these lesions has been performed safely for more than 50 years, many of these operations result in pulmonary insufficiency. For decades, it was believed that pulmonary insufficiency was a benign condition, as it is typically well tolerated throughout childhood and in many patients for several decades thereafter. Recently, however, it has been widely recognized that chronic pulmonary regurgitation (PR) in this patient population is associated with a number of pathologic conditions including: right ventricular dilation, diminished ventricular systolic function, arrhythmia, decreased functional capacity, right heart failure and death (1). Numerous surgical options exist for placing a competent valve in the pulmonic position (homografts, xenografts, bioprosthetic valves), however all of these options by definition require repeat open heart surgery and all of the attendant risks and morbidity associated with it (2). Furthermore, all currently available options for surgical pulmonary valve replacement are only temporizing in that essentially all of these valves will degenerate and need replacement (3, 4).

The durability of these prostheses is variable and time to reoperation often depends on the chosen conduit material and/or biological tissue and age of the patient at the time of the initial surgery. Thrombosis, recurrent stenosis and conduit tissue/valve leaflet calcification with concomitant PR are the most commonly reported reasons for additional surgical reinterventions. Patients receiving pulmonary xenografts are reported to have a mean time to reintervention of 10.3 years and for those implanted with a homograft 16 years. Multiple reoperations over a patient's lifetime are the current norm (3, 4).

Transcatheter replacement of the pulmonary valve, currently designed only to be used in the setting of a previously placed failed right ventricle-pulmonary artery (RV-PA) conduit, provides a less invasive alternative to surgical replacement, which requires open-heart surgery, re-sternotomy and cardiopulmonary bypass. Treatment of this patient population with a transcatheter heart valve (THV) may provide both short and long-term relief of their symptoms, improved hemodynamic function, and a gradual, consistent improvement of their cardiac function, which may delay the need for future repeat open-heart surgeries and provide improved quality of life (5) and might reduce the number of operations needed over the total lifetime of patients with RV-PA conduits (1, 2).

Currently there are two Food and Drug Administration (FDA) approved transcatheter pulmonic valves (TPV) for use as an adjunct to surgery in the management of patients with dysfunctional RVOT conduits. The Medtronic Melody Transcatheter Pulmonary Valve was approved on January 27, 2015 for use as an adjunct to surgery in the management of patients with

dysfunctional RVOT conduits. Due to its use of a bovine jugular vein, the Melody device can only be manufactured in sizes ≤ 22 mm for treatment of RVOT conduits ranging from 16-20 mm. The SAPIEN XT valve was approved in 2016 for use in the pulmonic position, also as an adjunct to surgery in patients with previously existing RV-PA conduits. The SAPIEN XT valve comes in diameters of 23, 26 and 29 mm. It is important to note that both of these devices are approved for use only in dysfunctional RV-PA conduits, not in patients who underwent other forms of RVOT surgery (e.g. pulmonary valvotomy, transannular patch repair). It is estimated that only 15% of congenital heart patients with RVOT dysfunction have had a previously placed surgical conduit resulting in the vast majority of these patients currently not being candidates for TPV implantation (TPVI) (6).

Currently there is no commercially-approved transcatheter valve available to treat patients with what is commonly referred to as a “native outflow tract”, meaning they have had their RVOT surgically addressed as described above (muscle resection, valvotomy/valvectomy and patch) but have not undergone conduit or other form of surgical pulmonary valve replacement. This is a challenging anatomic substrate to design a TPV due to several factors including: large diameter of the RVOT, irregular shape of the RVOT, marked changes in RVOT dimensions during systole and diastole, compliant nature and unpredictable shape of the RVOT after transannular patch. Several novel approaches have been described utilizing existing technologies; however, the larger population remains untreatable. Existing evidence suggests that if a proper “landing zone” can be created in the RVOT, one that reduces RVOT volume and creates a circular semi-rigid area to place a TPV, this patient population can be successfully treated and avoid repeated open heart surgery. Phillips et al reported on 8 patients with native RVOT who underwent successful TPVI after using a novel hybrid approach to modify the RVOT (7).

The Edwards Alterra Adaptive Presept (Alterra) is designed to provide a simple and safe way to reduce the diameter of these large irregular RVOTs and provide a circular, semi-rigid landing zone to place an Edwards SAPIEN 3 THV (8).

2 Study Objective

The objective of this study is to demonstrate the safety and effectiveness of the Edwards Alterra Adaptive Presept in conjunction with the Edwards SAPIEN 3 THV System in subjects with a dysfunctional RVOT/pulmonary valve (PV) who are indicated for treatment of PR.

3 Study Design

This is a single arm, prospective, multicenter study. Up to 60 subjects will be enrolled in the main cohort at up to 25 sites in the US and Canada. Twenty-five additional subjects will be enrolled in a separate registry to evaluate the Pulmonic Delivery System (PDS) for delivery of the SAPIEN 3 THV. No site will be allowed to enroll more than 35% of subjects (21 subjects in main cohort; 8 subjects in PDS Registry). Subjects will be assessed at the following intervals: screening/baseline, discharge, 30 days, 6 months, 12 months and annually thereafter through 10 years.

Subjects enrolled under EFS protocol versions 1.0 and 2.0 will count towards enrollment in the main cohort.

4 STUDY DEVICES

The following devices will be used in this trial:

- Edwards Alterra Adaptive PreStent, model 29AP4045
- Edwards Alterra Adaptive PreStent delivery system
- Edwards SAPIEN 3 THV, model 9600TFX in a 29 mm size
- Edwards Commander Delivery System, model 9600LDS29
- Edwards SAPIEN 3 Pulmonic Delivery System, model 9630PL29
- Edwards Crimper, model 9600CR
- Edwards Expandable Introducer Sheath Set, model 916ES
- Edwards Balloon Catheter, model 9350BC25 (at physician’s discretion)
- Inflation Devices

4.1 Investigational Device Descriptions

4.1.1 Edwards Alterra Adaptive PreStent

The preStent is used as a docking adaptor for the 29 mm SAPIEN 3 THV. It is comprised of a self-expanding, radiopaque, nitinol frame assembly and polyethylene terephthalate (PET) fabric covering. The preStent has designated inflow and outflow sides. The proximal inflow section is identifiable by the presence of two triangular tabs that are attached to the catheter of the delivery system. The distal outflow section is distinguished by the open cells for blood flow. The PET fabric is attached by sutures to the inside surface of the frame to create a sealing at the inflow section and opening for the outflow. Sutures are also used in the center to support the middle section when a SAPIEN 3 THV is implanted. Refer to **Table 1** for Alterra Device Sizing.

Figure 1: Edwards Alterra Adaptive PreStent

[figure not shown]

[figure not shown]
Table 1: Alterra Device Sizing

| Perimeter | Perimeter Derived Diameter* | Prestent Size | THV Size |
|------------------|-----------------------------|---------------|----------|
| 84.9 mm-119.3 mm | 27-38 mm | 40 mm x 48 mm | 29 mm |

* Diameter range throughout cardiac cycle

Edwards Alterra Delivery System

The delivery system includes a handle which consists of a wheel that allows for deployment, two primary shafts with a flush port to flush the delivery system, and a long compliant tapered tip at the distal end to facilitate tracking through the vasculature. The prestent is fully loaded in the delivery system. A stylet is included within the guidewire lumen.

Figure 2: Edwards Alterra Delivery System

4.1.2 Edwards SAPIEN 3 THV

The SAPIEN 3 THV is a catheter-delivered heart valve that combines a balloon expandable stent and bioprosthetic valve technology.

The SAPIEN 3 THV is comprised of a balloon-expandable, radiopaque, cobalt-chromium alloy frame, a tri-leaflet bovine pericardial tissue valve, a PET inner skirt, and a PET outer skirt. The valve tissue is treated according to the Edwards ThermoFix process, packaged and terminally liquid sterilized in a buffered glutaraldehyde solution.

The 29 mm SAPIEN 3 THV is intended to be implanted into the previously placed Alterra Adaptive Present within a dysfunctional RVOT.

4.1.3 Edwards Commander Delivery System

The Edwards Commander Delivery System includes:

- Edwards Commander Delivery System
- Loader
- Qualcrimp Crimping Accessory
- 2-piece Crimp Stopper

The Edwards Commander Delivery System consists of a balloon catheter for deployment of the THV and a Flex Catheter to aid in valve alignment to the balloon, tracking and positioning of the THV. The delivery system includes a tapered tip to facilitate crossing of the RVOT. The handle contains a Flex Wheel to control flexing of the Flex Catheter, and a Balloon Lock and Fine Adjustment Wheel to facilitate valve alignment and positioning of the valve within the RVOT. A stylet is included within the guidewire lumen of the delivery system. The Balloon Catheter has radiopaque Valve Alignment Markers defining the working length of the balloon. A radiopaque Center Marker in the balloon is provided to help with valve positioning. A radiopaque Triple Marker proximal to the balloon indicates the Flex Catheter position during deployment.

Loader

The loader is used to aid insertion of the delivery system into the sheath, and may be removed to utilize the full working length of the inserted device.

Qualcrimp Crimping Accessory

The Qualcrimp crimping accessory is a non-patient-contacting device that is designed to protect the SAPIEN 3 THV tissue leaflets during the crimping process. It is placed around the SAPIEN 3 THV during the crimping process to facilitate displacement of the valve tissue between the valve frame struts and to prevent potential tissue damage.

2-piece Crimp Stopper

This component is discussed in **Section 4.1.5**.

4.1.4 Edwards SAPIEN 3 Pulmonic Delivery System

The Edwards SAPIEN 3 Pulmonic Delivery System includes:

- Edwards SAPIEN 3 Pulmonic Delivery System
- 24F Dilator
- Qualcrimp Crimping Accessory
- 2-piece Crimp Stopper
- Lock Clip

The Edwards SAPIEN 3 Pulmonic Delivery System consists of an in-line sheath, balloon catheter for deployment of the Edwards SAPIEN 3 THV, and an outer shaft to cover the THV during insertion and tracking to the intended deployment location. The delivery system includes a tapered tip to facilitate crossing of right heart structures. A radiopaque Center Marker in the balloon is provided to help with valve positioning. A stylet is included within the guidewire lumen of the delivery system.

Dilator

The 24F Dilator (packaged with the delivery system) is used to predilate the vessel prior to insertion of the delivery system, if necessary.

Qualcrimp Crimping Accessory

The Qualcrimp crimping accessory (packaged with the delivery system) is used during crimping of the THV.

2-piece Crimp Stopper

This component is discussed in **Section 4.1.5**.

Lock Clip

The Lock Clip (packaged with the delivery system) is used to maintain the position of the outer shaft during delivery system insertion.

4.1.5 Edwards Crimper

The Crimper reduces the diameter of the SAPIEN 3 THV to mount it to the delivery system. The Crimper is comprised of a compression mechanism that is closed with a handle located on the housing. The Crimper is used with a 2-piece Crimp Stopper (packaged with the delivery system) to correctly crimp the THV to the appropriate size.

4.2 Intended Use

The Edwards Alterra Adaptive Presept, used in conjunction with the 29 mm Edwards SAPIEN 3 THV, is intended for use in the treatment of moderate to severe PR in pediatric and adult patients with a dysfunctional RVOT/PV.

5 STUDY ENDPOINTS

5.1 Primary Endpoint

Main Cohort:

The primary endpoint is THV dysfunction at 6 months. THV dysfunction is defined as a non-hierarchical composite of:

- RVOT/PV reintervention
- Moderate or greater total PR via Transthoracic Echocardiography (TTE)
- Mean RVOT/PV gradient \geq 35 mmHg via TTE

PDS Registry:

The primary endpoint is Acute PDS Success, defined as a non-hierarchical composite of:

- Single THV implanted in the desired location
- RV-PA peak-to-peak gradient $<$ 35 mmHg post-THV implantation
- Less than moderate total PR by discharge TTE (or earliest evaluable TTE)
- Free of SAPIEN 3 / Alterra explant at 24 hours post-implantation

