10.3 Primary Endpoint Analysis

Main Cohort:

The primary endpoint is THV dysfunction at 6 months. THV dysfunction is defined as a non-hierarchical composite of:

- RVOT/PV reintervention
- Moderate or greater total PR via TTE (as assessed by Echo Core Lab)
- Mean RVOT/PV gradient ≥ 35 mmHg via TTE

The observed proportion with THV dysfunction and a two-tailed exact binomial 95% CI will be calculated for the composite endpoint as well as each of the individual components.

A performance goal of 25% was pre-specified for the 6-month rate. The hypothesis for the primary endpoint is as follows:

$$H_0: \pi_{\text{Alterra}} \geq 25\%$$

$$H_A: \pi_{\text{Alterra}} < 25\%$$

Where π_{Alterra} represents the proportion of subjects with THV dysfunction at 6 months. If the upper 95% confidence limit for the composite event is less than 25%, the performance goal will have been met.

The primary endpoint will be evaluated on the VI population.

PDS Registry:

The primary endpoint is Acute PDS Success, defined as a non-hierarchical composite of:

- Single THV implanted in the desired location
- RV-PA peak-to-peak gradient < 35 mmHg post-THV implantation
- Less than moderate total PR by discharge TTE (or earliest evaluable TTE)
- Free of SAPIEN 3 / Alterra explant at 24 hours post-implantation

No formal hypothesis testing will be conducted. Data will be analyzed by descriptive summary tables only.

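### The PDS Registry's primary endpoint does not isolate PDS performance: a failed PDS delivery completed with another delivery system would score as PDS success

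*Combined protocol and SAP*

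**What the plan says.** The purpose of the registry is given in Section 3 and repeated in the synopsis: "Twenty-five additional subjects will be enrolled in a separate registry to evaluate the Pulmonic Delivery System (PDS) for delivery of the SAPIEN 3 THV".

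Section 5.1 states for the registry: "The primary endpoint is Acute PDS Success, defined as a non-hierarchical composite of" four items. The same four items appear in the synopsis, Section 5.1 and Section 10.3:

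- "Single THV implanted in the desired location";
- an RV-PA peak-to-peak gradient below "35 mmHg post-THV implantation";
- total PR less than moderate on the discharge TTE, or the earliest evaluable one;
- "Free of SAPIEN 3 / Alterra explant at 24 hours post-implantation".

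Appendix B defines Device Success but has no entry for PDS success. Section 4 lists two systems that can deliver the THV: the PDS and the "Edwards Commander Delivery System, model 9600LDS29". It does not assign either to a cohort.

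Section 10.2 counts a subject as enrolled from vascular access for the Alterra procedure and defines the AT, AI and VI populations. None of these refers to the PDS. Section 10.3 names the VI population for the main cohort's primary endpoint, names none for the registry, and limits the registry analysis to descriptive tables.

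**The concern.** The composite carries the name of a delivery system but measures the state of the valve afterwards. Compared with the main cohort's Acute Device Success (Section 5.3), it drops the single-Alterra item and the requirement that the valve lie within the Alterra, and it extends the explant item to the SAPIEN 3. Nothing about delivery was added.

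If the PDS is withdrawn without delivering the valve and one valve is then placed with another system, the subject can meet every item. The reported rate then describes implant success by whatever route was used. The registry has no comparator, threshold or hypothesis test, so the meaning of its main result rests on this definition alone.

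**Working it through.** **The plan's own figures.** The registry has no power, precision or performance-goal figure to reproduce, only n = 25. The one power calculation (Section 10.1) concerns the main cohort. It reproduces: rejecting at 4 or fewer events in 38 gives P(X ≤ 4 | 0.25) = 0.0235 and P(X ≤ 4 | 0.074) = 0.8531. It does not bear on this point.

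**Step 1: apply the definition to a switched case.** Suppose the PDS cannot deliver the valve, is withdrawn, and one THV is placed with another system with a good result.

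| Item | Names a delivery system? | Switched case |
|---|---|---|
| Single THV in desired location | No | Met |
| Gradient < 35 mmHg | No | Met |
| Less than moderate total PR | No | Met |
| No SAPIEN 3 / Alterra explant at 24 hours | No | Met |

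The case scores as Acute PDS Success. The registry's additional outcomes (Section 5.3) are TR improvement, major vascular complications, bleeding, and embolization of the Alterra or THV. None records which system was used.

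**Step 2: size.** Inputs: n = 25 (Section 3) and r switched cases. The documents give no value for r, so it is an assumption. Assume also that every switched case meets the four items and that all other subjects are successes.

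Reported rate = 25/25. PDS-specific rate = (25 − r)/25. Overstatement = r/25, or 4 percentage points per case. Intervals are exact (Clopper-Pearson) 95%; for 25/25 the lower limit is 0.025^(1/25) = 86.3%.

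| r | As written | If delivery with the PDS is required |
|---|---|---|
| 0 | 100% (86.3–100) | 100% (86.3–100) |
| 1 | 100% (86.3–100) | 24/25 = 96% (79.6–99.9) |
| 2 | 100% (86.3–100) | 23/25 = 92% (74.0–99.0) |
| 3 | 100% (86.3–100) | 22/25 = 88% (68.8–97.5) |
| 5 | 100% (86.3–100) | 20/25 = 80% (59.3–93.2) |

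**Step 3: the other direction.** Enrollment starts before any PDS use. If all enrolled subjects form the denominator, one Alterra failure before any PDS attempt leaves no THV in place and counts as a PDS failure: 24/25 = 96%. Among subjects with a PDS attempt, the same data give 24/24 = 100%. If the VI population were used instead, a failed PDS delivery that ended with no valve would leave the denominator altogether. Because no registry population is stated, the direction of the net error is not fixed.

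**The case against.** The strongest reply has five parts.

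- **Many PDS failures are still caught.** A second implanted valve, a wrong location, a high gradient, moderate PR or an explant fails the composite. Embolization and vascular complications are 30-day outcomes. Malfunctions are reportable with or without an AE (Section 8.5), and an implant procedure report is required for every enrolled subject (Section 8.2). This stands. A reader might infer that the registry cannot evaluate the PDS at all; the documents do not support that. What is missing is a scoring rule in the endpoint and a pre-specified table outside it.
- **The switch is a constructed scenario.** This stands in part. No text describes one, and Section 7.3.3 ties device use to labeling that is not among the documents. But Section 9.2 lists mechanical failure of the delivery system as a risk, so the endpoint needs a rule for it.
- **The error need not favour the PDS.** This stands. A reader might infer a one-sided bias, but Step 3 shows that the composite can also count non-PDS failures against the PDS.
- **The chance of misclassification is unknown.** This stands. A reader might assume a 5% or 10% delivery-failure rate and compute 1 − 0.95^25 = 72% or 1 − 0.90^25 = 93%. Those are chances of at least one delivery failure. Misclassification also needs a switch and all four items met, so its probability is lower and cannot be derived here.
- **Some of this is definitional choice, and the registry is descriptive.** Both stand. Whether a second PDS unit or a retrieval problem after good deployment is a failure is for the sponsor to define. No error rate or formal conclusion changes.

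**Conclusion.** The point holds in this form: Acute PDS Success does not isolate PDS performance. Applied as written, it counts a failed PDS delivery completed with another system as PDS success whenever the four valve-result items are met. This follows from the text and needs no assumption.

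The size does rest on assumptions. Each such case is worth 4 percentage points in 25, so one to three cases give a reported 100% against 96%, 92% or 88%. The documents give neither a failure rate nor a rule on switching, so these figures illustrate the effect and do not predict it. With the denominator unstated, Alterra failures before PDS use could also lower the rate. The consequence is limited to the interpretation of a descriptive rate, but that rate is the registry's primary result.

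**What to change.** 1. In the synopsis, Section 5.1 and Section 10.3, add a fifth item to Acute PDS Success: *THV delivered and deployed with the PDS, without use of another delivery system*. This concerns scoring only; it takes no position on whether a switch should be allowed.
2. In Section 10.2, define a registry population of all registry subjects with attempted PDS insertion, fixing the moment of attempt as is already done for the Alterra in the AI population. Report Alterra failures before any PDS attempt separately.
3. Pre-specify a descriptive table of PDS malfunctions, including use of more than one PDS and retrieval problems, without making these endpoint failures by default.

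The cost is one eCRF field for the delivery system used, which can be checked against the implant procedure report already required by Section 8.2, and a reported success rate that may be lower. No sample size, alpha or test changes.
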